6.4 Study Primary and Secondary Objectives

The purpose of this study is to evaluate the effects of daratumumab with dexamethasone in subjects with relapsed or refractory multiple myeloma and renal impairment.

Primary objective(s)

The primary objective of this study is to evaluate progression free survival (PFS) in subjects with relapsed or refractory multiple myeloma and renal impairment treated with daratumumab and dexamethasone.

Secondary objective(s)

The secondary objectives of the study are the following:

- To evaluate Overall Response Rates (ORR)
- To evaluate Renal Response Rates (RRR)
- To evaluate duration of response in patients with RI.
- To evaluate time to next therapy.
- To evaluate Overall Survival (OS).
- To assess the safety and tolerability of Daratumumab with dexamethasone in patients with RRMM and RI.

6.4.1 Study Primary and Secondary Endpoints

Primary endpoint:

- Progression-free survival

Secondary endpoints

- Overall response rate
- Renal Response rate
- Duration of response
- Time to next therapy
- Overall survival
- Safety (adverse events)

6.4.2 Sample Size and Power Calculations

The calculations were based on previous data for daratumumab in patients with relapse or refractory myeloma. The median Progression Free Survival (PFS) with daratumumab treatment in the SIRIUS study was 5.6 months in patients who received daratumumab at the dose of 16 mg/kg.

Health Data Specialists	
DARE (EAE-2017/MM02)- Statistical Analysis Plan	Version: 1.0 EN
Author: GC, Reviewer: MS, Quality Assurance: GK	Date: 02-02-2018

In order to test at $\alpha=0.05$ the null hypothesis that the PFS is less than 3 months versus the alternative hypothesis that PFS is at least 5 months with a power of 90%, 34 patients must be included in the study. This calculation assumes exponential survival curves, an accrual time of 18 months and a length of follow up period of 30 months. Assuming a drop-out rate of about 10%, 38 patients are needed.

Sample size was computed by “SWOG One arm survival sample size and power” (www.swogstat.org/stat/public/one_survival.htm)

6.5 Population of Analysis Sets

6.5.1 Full Analysis Set (FAS)

The FAS comprises all patients to whom study treatment has been assigned according to the intent to treat principle.

6.5.2 Per Protocol Analysis Set (PPS)

The PPS consists of a subset of patients in the FAS who received at least one dose of the study drug and had no major protocol deviation. Protocol deviations leading to exclusion from the PPS will be defined in the Statistical Analysis Plan.

6.5.3 Safety Set

The Safety Set consists of all patients who received at least one dose of study treatment. Patients who have been randomized and did not take at least one dose of study treatment will not be included in the safety set. Patients will be analyzed according to the study treatment they actually received.

6.5.4 Subgroups

In this study, no sub group analysis was planned to be performed within the primary and secondary endpoints analysis. However, it is considered necessary to further examine the data that will be collected, in order to provide insights for this non-in depth investigated population. Hence, additional subgroup and exploratory analyses will be performed (see 6.6). The following subgroups will be used for the additional analyses:

- ISS stage at the time of diagnosis
- Revised ISS stage at the time of diagnosis
- eGFR (< 15 vs ≥ 15 at baseline)
- Patients with at least one eGFR>30 measurement over the whole observation period vs patient without such a measurement
- ECG (normal vs at least one abnormality)
- Prior treatments (2-5 treatments vs >5 treatments)
- LDH ()
- FISH risk (low risk, standard risk, intermediate risk & high risk) (1)
- Age at diagnosis (<60 vs. ≥ 60).
- MRD negativity (negative vs. positive).

Health Data Specialists	
DARE (EAE-2017/MM02)- Statistical Analysis Plan	Version: 1.0 EN
Author: GC, Reviewer: MS, Quality Assurance: GK	Date: 02-02-2018

6.5.5 Interim Analysis

N/A

6.6 Statistical Methodology

All statistical analyses will be performed using SAS® version 9.4 (64-bit) or later, a validated statistical software package, (SAS Institute, Inc., Cary, NC, USA).

Data from all sites will be pooled and summarized. Continuous data will be summarized by mean, standard deviation (SD), median, first and third quartiles, minimum and maximum. Categorical data will be presented by absolute and relative frequencies (n and %) or contingency tables.

One-sided alpha level 0.025 will be considered. No alpha level adjustment will be carried out for primary and secondary outcome variables.

The primary efficacy endpoint is PFS for patients, who received daratumumab at the dose of 16 mg/kg, as assessed by the Investigator. The distribution of PFS will be estimated using the Kaplan-Meier method. The median PFS along with 95% confidence intervals will be presented (see Section 6.6.1.3). The analysis will be performed when at least 20 PFS events have been documented.

6.6.1 Methods of Statistical Analyses

All data regarding patient demographics and baseline characteristics will be summarized on the FAS, overall, by means of summary descriptive statistics.

A complete description of patient disposition will be provided, specifying the number of enrolled patients, number of patients at each visit, completed and discontinued patients, and the reason for the discontinuation.

The analysis populations will be described and the reasons for excluding the patient from any analysis set will be provided with the number of protocol violators per each criterion.

Medical history data will be presented by MedDRA System Organ Class and Preferred Term.

Descriptive statistical analysis will be performed for all study data and epidemiological methods will be applied. Continuous variables will be summarized with the use of descriptive statistical measures [mean value, standard deviation (SD), median and range] (Table 2). Categorical/distinct variables will be displayed as frequency tables (N, %) (Table 3), by group.

Additional sub-group analyses will be performed. The basic demographic characteristics, the primary and the secondary endpoints will be summarized by group. Between groups comparisons will be performed. The sub groups that will be used are derived based on known risk factors that are associated either with the MM or with the RR. Hence, all the endpoints will be analyzed in the following subgroups:

Health Data Specialists	
DARE (EAE-2017/MM02)- Statistical Analysis Plan	Version: 1.0 EN
Author: GC, Reviewer: MS, Quality Assurance: GK	Date: 02-02-2018

- ISS stage at the time of diagnosis
- Revised ISS stage at the time of diagnosis
- ECG (normal vs at least one abnormality)
- Prior treatments (2-5 treatments vs >5 treatments)
- LDH ()
- FISH risk (low risk, standard risk, intermediate risk & high risk) (1)
- Age >60 vs ≤60
- MRD negativity (negative vs. positive).

Additional exploratory analyses will be performed, in order:

- To compare the PFS, the OS, the ORR and the number of prior treatments at baseline (2-5 treatments vs >5 treatments) between patients with eGFR < 15 vs ≥15 at baseline.
- To compare the PFS, the OS, the ORR and the number of prior treatments at baseline (2-5 treatments vs >5 treatments) between patients with at least one eGFR>30 measurement over the whole observation period vs patient without such a measurement
- To compare the PFS, the OS, the ORR and the number of prior treatments at baseline (2-5 treatments vs >5 treatments) between patients with observed renal response and patients without renal response
- To evaluate if the FISH risk and renal response, measured as RRR are correlated.
- To evaluate if the FISH risk and renal response, using as cut-off point the eGFR>30, are correlated.
- To evaluate if the FISH risk and Prior treatments (2-5 treatments vs >5 treatments) are correlated

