Daratumumab in combination with dexamethasone is not approved for the indication under study. In November 2015, daratumumab (DARZALEX®) as monotherapy was approved by the U.S. Food and Drug Administration (FDA) for the treatment of patients with multiple myeloma who have received at least three prior lines of therapy, including a proteasome inhibitor (PI) and an immunomodulatory drug (IMiD), or who are double-refractory to a PI and an immunomodulatory agent. This indication was approved under accelerated approval based on the results of the pivotal open-label Phase 2 MMY2002 (SIRIUS) study in which treatment with single-agent daratumumab resulted in an Overall Response Rate (ORR) of 29.2 percent (95% CI; 20.8, 38.9). Median duration of response was 7.4 months (95% CI, 5.5-not estimable). Ninety-five percent of patients in the study were double refractory to a PI and IMiD and patients had received a median of five prior lines of therapy. No patients discontinued treatment due to infusion-related reactions (IRR) and 4.7 percent of patients discontinued treatment due to adverse events (AEs), none of which were considered drug-related. Stringent complete response (sCR) was reported in 2.8 percent of patients, very good partial response (VGPR) in 9.4 percent of patients, and partial response (PR) in 17 percent of patients. The most common adverse events, which occurred in more than 20 percent of patients, were fatigue, anemia, nausea, thrombocytopenia, back pain, neutropenia and cough.

These results were supported by those of the Phase 1/2 GEN501 study, which confirmed daratumumab as an effective single-agent treatment option for patients with relapsed and refractory myeloma, especially those with disease that is otherwise resistant to other treatments or those who have unacceptable side effects from other treatments. Daratumumab had an acceptable safety profile, with infusion-related reactions of grade 1 and 2 across the two dose cohorts (except for one patient with infusion-related reactions of grade 3), including mild and transient bronchospasm, headache, dyspnea, and fever. Most events occurred during the first infusion, and no patient discontinued treatment because of an infusion-related reaction. Daratumumab demonstrated a 36 percent ORR in patients treated with a 16 mg/kg dose, with responses improving (or “deepening”) over time.

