**Table 7.1 – Disease assessments**

M-protein by electrophoresis Serum (sPEP), Urine (uPEP)	Screening and baseline Day one of each cycle End of treatment Post-treatment follow-up every 4 weeks As needed to confirm disease progression
M-protein by immunofixation Serum (sIFE), Urine (uIFE)	Screening and baseline End of treatment Post-treatment follow-up every 4 weeks As needed to confirm CR (when PEP is 0 or non-quantifiable)
Serum free light chain sFLC	Screening and baseline Day one of each cycle (for patients that have no measurable serum or urine M-protein) As needed to confirm sCR End of treatment Post-treatment follow-up every 4 weeks As needed to confirm disease progression
Clinical assessment of soft tissue plasmacytoma (STP)	Screening and baseline Day one of each cycle End of treatment Post-treatment follow-up every 4 weeks As needed to confirm disease progression
CT/MRI assessment of STP	If present or suspected, at screening and as clinically indicated.
Plasma cell count in bone marrow	At screening and during the study as clinically indicated to substantiate CR and PD for patients with non-measurable disease by M protein in serum and urine as well as by FLC.
Skeletal survey by X-ray and/or CT/MRI	At screening and as clinically indicated, CT/MRI in case of newly symptomatic areas with no X-ray finding.
Serum Creatinine (for patients not on dialysis)	Screening and baseline Weekly in the first two cycles then every two weeks for cycles 3-6 and then on day one of each cycle End of treatment Post-treatment follow-up every 4 weeks
Corrected calcium	Screening and baseline Day one of each cycle End of treatment Post-treatment follow-up every 4 weeks As needed to confirm disease progression
MRD by means of EuroFlow next generation cytometry	If required for confirmation of sCR, upon confirmed CR/sCR and thereafter every 6 months as long as CR/sCR is maintained.

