#### **7.1.1.6 Minimal residual disease (MRD) by means of next generation flow cytometry (EuroFlow protocol).**

The EuroFlow-International Myeloma Foundation (IMF) next generation flow MRD approach provides a fast, highly applicable, ultrasensitive, standardized and accurate approach for the assessment of MRD in bone marrow samples from MM patients. MRD will be analyzed upon confirmed complete response and every 6 months thereafter until progression.

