sPEP, uPEP 	X	X				X				X					X	X													
sIFE, uIFE 	X	X			X				X						X	X													
			To confirm CR regardless of whether measurable M-protein was present at baseline. See Section 7.1.1.1																										
sFLC assay, $\kappa/\lambda$ ratio 	X	X			X				X						X	X													
			Analyzed only when serum M-protein or urine M-protein or both assessed by PEP is/are non-measurable and to identify sCR in case CR criteria are met. See Section 7.1.1.2																										
Plasma cell count in bone marrow	X	Plasma cell count during the study as clinically indicated to qualify for CR and PD for patients with non-measurable disease by M protein in serum and urine as well as by FLC. See Section 7.1.1.3																											
MRD		As per institution's practice at complete response or better and thereafter every 6 months as long as CR/sCR is maintained through EuroFlow cytometry. See Section 7.1.1.6																											
Corrected calcium 	X	X			X				X						X	X													
Skeletal survey 	X	As clinically indicated; CT/MRI in case of newly symptomatic areas with no X-ray finding. See Section 7.1.1.6																											
Assessment of extramedullary soft tissue plasmacytoma	X	Clinical assessment on day one of each cycle at the End of treatment and at Post treatment follow-up every 4 weeks. CT or MRI at screening only if there are STP findings during the clinical assessment or documented evidence from previous imaging assessments and as clinically indicated. See Section 7.1.1.4																											
Response assessment by Investigator		C2D1			X				X						X	X													
Treatment																													
Daratumumab		X	X	X	X	X		X			X																		
Dexamethasone		X	X	X	X	X	X	X	X	X	X	X	X	X															
		40 mg (20 mg for patients > 75 years of age) orally, weekly																											

Day of Cycle (28-days)	Screening ^	Treatment: visit window during the treatment period is +/- 3 days												End of treatment EOT 	Post treatment FU Every 4 weeks 	Survival follow-up Every 12 weeks		
		Cycles 1 and 2				Cycles 3-6				Cycles 7 and beyond								
		-21 to 1	1 BL	8	15	22	1	8	15	22	1	8	15	22				
Other anti-neoplastic therapies		Not permitted												X	X	X		
Survival follow-up																X		

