Analyzed only when serum M-protein or urine M-protein or both assessed by PEP is/are non-measurable and to identify sCR in case CR criteria are met. See Protocol; Section 7.1.1.2																
Plasma cell count in bone marrow	X	Plasma cell count during the study as clinically indicated to qualify for CR; and PD for patients with non-measurable disease by M protein in serum and urine as well as by FLC. See Protocol; Section 7.1.1.4														
MRD		As per institution's practice at complete response and thereafter as clinically indicated through EuroFlow cytometry. See Protocol; Section 7.1.1.6														
Corrected calcium ⁶	X	X			X			X			X			X	X	
Skeletal survey ⁷	X	As clinically indicated; CT/MRI in case of newly symptomatic areas with no X-ray finding. See Protocol; Section 7.1.1.6														
Assessment of extramedullary soft tissue plasmacytoma	X	Clinical assessment on day one of each cycle at the End of treatment and at Post treatment follow-up every 4 weeks. CT or MRI at screening only if there are STP findings during the clinical assessment or documented evidence from previous imaging assessments and as clinically indicated. See Protocol; Section 7.1.1.4														
Response assessment by Investigator		C2D1			X				X					X	X	
Treatment																
Daratumumab		X	X	X	X	X		X		X						
Dexamethasone		X	X	X	X	X	X	X	X	X	X	X	X			
40 mg (20 mg for patients > 75 years of age) orally, weekly																
Other anti-neoplastic therapies		Not permitted												X	X	X
Survival follow-up																X

[^] The majority of screening assessments are to be performed within 21 days from the date of ICF signature until C1D1. See Protocol; [Section 7.2.1](#) for details.

⁰ i In addition to ABO and Rh blood typing, indirect antiglobulin test (also known as indirect Coombs test) will be performed; it is recommended that the subject carries a card with the blood antigen profile at all times during the study.

¹ Women of childbearing potential (WOCBP) must have two negative serum or urine pregnancy tests, one 10-14 days prior to start of the study drug and one within 24 hours prior to the start of study drug.² M protein by electrophoresis in serum (sPEP) and urine (uPEP). Serum on Day 1 of each cycle until disease progression. 24-hour urine sample can be collected within ± 7 days of visit.

³ M protein by immunofixation in serum (sIFE) and urine (uIFE). ⁴ Free light chain protein assessment (sFLC)

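### The SAP compares all endpoints between MRD-negative and MRD-positive patients, but MRD is tested only at complete response or better, so the comparison is uninformative for ORR and undefined for everyone else

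*SAP*

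**What the plan says.** SAP 6.5.4 lists "MRD negativity (negative vs. positive" among the subgroups for additional analyses. SAP 6.6.1 repeats the item, describes the subgroups as derived from known risk factors, and says "Between groups comparisons will be performed" and "Hence, all the endpoints will be analyzed in the following subgroups". Neither list has a level for patients without an MRD result.

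MRD testing is described in four places:

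- Protocol 7.1.1.6: "MRD will be analyzed upon confirmed complete response and every 6 months thereafter until progression".
- Protocol Table 7.1: "If required for confirmation of sCR, upon confirmed CR/sCR and thereafter every 6 months as long as CR/sCR is maintained".
- Protocol Table 7.2, which refers to institutional custom: "practice at complete response or better and thereafter every 6 months as long as CR/sCR is maintained".
- SAP 6.3 (Table 1), also by institutional custom: "practice at complete response and thereafter as clinically indicated through EuroFlow cytometry".

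The first two require a confirmed CR; the two schedule tables do not use that word. None schedules a test at baseline or for a patient whose response is below CR.

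ORR counts a best response of PR or better (SAP 6.6.1.4). PFS and time to next therapy run from Cycle 1 Day 1 and OS from the first dose (SAP 6.6.1.3 and 6.6.1.4).

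**The concern.** A subgroup factor should be known for essentially every patient and, for comparing times counted from treatment start, known at that start. MRD here meets neither condition. It is a result that exists only after treatment has produced a CR.

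This has three consequences:

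- For ORR, membership of either tested group already implies response, so the comparison is settled before any data are seen.
- For the other endpoints, patients with VGPR, PR, MR, stable or progressive disease have no value, and the SAP does not say what to do with them.
- For PFS and OS, groups are formed by a later event with no landmark. MRD may also be repeated, and the SAP does not say which result assigns the group.

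What is at stake is a table that either carries no information or, if untested patients are placed in the positive group, presents the difference between complete responders and all other patients as an effect of MRD.

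**Working it through.** **Inputs**

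- Planned enrolment is 38 (SAP 6.4.2). This reproduces as 34 / (1 − 0.10) = 37.8, rounded up to 38.
- The single-agent study that underlies the sample size is described in Protocol 1.2: "Stringent complete response (sCR) was reported in 2.8 percent of patients", with VGPR 9.4%, PR 17% and ORR 29.2% (95% CI 20.8 to 38.9). Since 2.8 + 9.4 + 17 = 29.2, nothing is left for non-stringent CR, and CR or better is 2.8%.
- Protocol 1.2 also gives CR-or-better rates of 19% (with bortezomib and dexamethasone, median two prior lines) and 43% (with lenalidomide and dexamethasone, median one prior line).
- The documents state no expected number of MRD-tested patients and no CR rate for this regimen in this population. The 10% below is an assumption.

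**Step 1: ORR in the tested groups.** Tested implies CR or sCR, and CR or sCR implies PR or better. ORR is therefore 100% in the negative group and 100% in the positive group. No CR rate enters this step.

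**Step 2: uncertainty of the 2.8%.** The study's denominator is not stated. A count of 31/106 reproduces 29.2% with an exact interval of 20.8% to 38.9%, so 106 is inferred, and 2.8% corresponds to 3/106. Its exact 95% CI is 0.6% to 8.0%.

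**Step 3: number tested.** With CR rate p:

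- expected number tested = 38p
- P(0 or 1 tested) = (1 − p)^38 + 38p(1 − p)^37

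For p = 0.028 this is 0.340 + 0.372 = 0.712. For p = 0.10 it is 0.018 + 0.077 = 0.095.

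| CR rate | Source | Expected tested | P(0 or 1 tested) | Expected without MRD result |
|---|---|---|---|---|
| 0.6% | lower limit, inferred 3/106 | 0.2 | 98% | 37.8 |
| 2.8% | single agent | 1.1 | 71% | 36.9 |
| 8.0% | upper limit, inferred 3/106 | 3.1 | 18% | 34.9 |
| 10% | assumption | 3.8 | 9.5% | 34.2 |
| 19% | triplet | 7.2 | below 1% | 30.8 |
| 43% | triplet | 16.3 | below 1% | 21.7 |

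Two tested patients are the minimum for two filled groups, but they do not guarantee them. If tested patients split evenly between negative and positive (an assumption), P(both groups filled) = 1 − 2(1 − p/2)^38 + (1 − p)^38. This is 17% at 2.8%, 62% at the upper limit of 8.0%, and 95.5% at 19%.

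**Step 4: untested patients coded positive.** Everyone is then classified. ORR stays at 100% in the negative group, while the positive group mixes MRD-positive complete responders with all patients below CR. A patient enters the negative group only by remaining alive and progression-free until CR and the MRD test, yet PFS and OS are counted from treatment start. That waiting time is credited to the negative group, which is immortal-time bias in its favour.

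**The case against.** The strongest defence is that the documents do not fix the outcome as firmly as a reader might infer. Three stronger readings are tempting.

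- *Nearly everyone falls in neither group, and ORR is 100% in both groups, full stop.* This holds only if untested patients are left out. The SAP states no rule either way. If they were coded positive, both statements would fail, but Step 4 applies instead.
- *About one patient will be classifiable, and one group will usually be empty.* This rests on the single-agent 2.8%, from patients with a median of five prior lines, 95% of them double refractory. This trial adds dexamethasone and admits patients after two lines. At 10% the chance of 0 or 1 tested falls from 71% to 9.5%. The triplet rates come from less pretreated patients on other regimens, so they show how far the count could move and are not forecasts for this trial.
- *MRD is tested only once CR is confirmed.* Protocol 7.1.1.6 and Table 7.1 say so, but Protocol Table 7.2 and SAP Table 1 do not. A patient tested at an unconfirmed CR whose repeat shows VGPR or PR is still a responder, so the ORR result barely depends on this. Testing by institutional custom could lower the count further.

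It is also fair that SAP 6.5.4 calls these analyses additional, and that MRD is neither an objective nor an endpoint. A sparse table would reveal itself, and an MRD-negative rate from few patients says little: 0/38 has an exact 95% CI of 0 to 9.3%.

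These points limit the size and severity of the concern. They do not rescue the comparison, because no text in either document makes MRD available below CR or makes ORR vary among tested patients.

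**Conclusion.** The concern holds in a bounded form. Under either handling of untested patients, the planned comparison does not measure what its label says:

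- If they are excluded, ORR is 100% against 100% at any CR rate, and all patients below CR drop out.
- If they are coded positive, MRD-negative complete responders are set against everyone else, with immortal-time bias in PFS and OS.

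The number tested is not known in advance. It is about 1.1 of 38 if the single-agent rate carries over (0.2 to 3.1 over the inferred interval), 3.8 at an assumed 10%, and 7.2 to 16.3 at the triplet rates. Even at the highest of these, about 22 of 38 patients (38 − 16.3) have no MRD result.

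A reader might infer that the trial's conclusions are at risk. They are not: the primary PFS analysis and the sample size do not use MRD. Severity is minor.

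**What to change.** Remove MRD from the between-group subgroup lists in SAP 6.5.4 and 6.6.1. In its place, report descriptively:

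- the number of patients tested;
- the MRD-negative rate in the FAS, counting untested patients as not negative, with an exact two-sided 95% CI;
- a listing of PFS and DoR for each tested patient, with the date of the MRD result.

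This needs SAP wording only. It uses data already being collected and rules out coding untested patients as positive. The cost is the exploratory MRD-negative versus MRD-positive comparison among complete responders. The rate will be imprecise if few patients are tested, so it should be labelled descriptive.

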### Survival follow-up

Subjects will be followed every 12 weeks, or more frequently, after disease progression for survival and subsequent myeloma therapy until the end of study.

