6.6.1.3 Primary Endpoint Analysis

The efficacy analysis will be performed based on the FAS as primary analysis and on the PPS as supportive analysis.

Progression Free Survival (PFS)

PFS is defined as the time, in months, from treatment initiation (Cycle 1 , day 1) to the date of the first documented tumor progression or death due to any cause, whichever comes first. Clinical deterioration will not be considered progression. For subjects who neither progress nor die, the survival time will be censored at the date of their last tumor assessment. For subjects who start a new anti-tumor treatment, survival time will be censored at the date of the start of the new treatment.

The PFS function will be estimated using the Kaplan-Meier product-limit method. Median and two-sided confidence intervals (CI) for median PFS will be computed by and Kaplan-Meier plots of PFS will be presented.

Absolute frequencies and proportions of patients with tumor progression or all-cause death will also be provided.

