APPENDIX 1) as their best overall response.

The response rate, along with its exact two-sided 95% CI, will be computed.

Renal Response Rate (RRR)

Rrr is defined as the proportion enrolled subjects who achieve a best response of renal partial renal response (PRRenal) or better using the criteria of the International Myeloma Working Group (IMWG) (APPENDIX 2).

Duration of Response (DoR)

DoR will be restricted to the subjects that achieve a best objective response of PR or better. It is measured from the time, in months, that the criteria for objective response are first met until the date of a progression event (according to the primary definition of PFS). A subject with objective response who does not have a progression event will be censored at the same time they were censored under the primary definition of PFS.

The DoR function will be estimated using the Kaplan-Meier product-limit method. Median and two-sided confidence intervals for median duration of response will be computed and Kaplan-Meier plots of DoR will be presented.

Time to Next Therapy (TNT)

TNT will be defined as the time, in months, from Cycle 1 Day 1 to the date to next anti-neoplastic therapy or death from any cause, whichever comes first. For subjects who neither start a new anti-neoplastic therapy nor die, survival time will be censored at the date of their last available follow-up assessment.

Time to next therapy will be calculated using a log-rank test procedure. The TNT function will be estimated using the Kaplan-Meier product-limit method. Median and two-sided confidence intervals for median TNT will be computed. Kaplan-Meier plots of TNT will be presented.

Overall Survival (OS)

Overall survival is defined as the time, in months, from the first dose of therapy to the date of death from any cause. If a patient is not known to have died, survival time will be censored at the date of last contact (“last known date alive”).

Overall survival will be estimated using the Kaplan-Meier product-limit method. Median and corresponding two-sided 95% confidence intervals will be computed. Kaplan-Meier plots of OS will be presented.

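### Two exploratory PFS and OS comparisons group patients by renal recovery seen after the clock starts, so they favour the recovery group even when there is no true association

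*SAP*

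**What the plan says.** The additional exploratory analyses in SAP 6.6.1 are each introduced with "To compare the PFS, the OS, the ORR and the number of prior treatments at baseline". Two of them form their groups from data collected after baseline:

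- by eGFR: "between patients with at least one eGFR>30 measurement over the whole observation period vs patient without such a measurement". SAP 6.5.4 lists the same subgroup: "Patients with at least one eGFR>30 measurement over the whole observation period vs patient without such a measurement".
- by renal response: "between patients with observed renal response and patients without renal response". SAP 6.6.1.4 and Appendix 2 define this as the best eGFR reached relative to baseline.

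The clocks start earlier. SAP 6.6.1.3: "PFS is defined as the time, in months, from treatment initiation". SAP 6.6.1.4: "Overall survival is defined as the time, in months, from the first dose of therapy".

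Entry requires eGFR below 30 or need for dialysis (Protocol 5.1; SAP 6.1.1). Protocol Table 7.1 schedules creatinine "Weekly in the first two cycles then every two weeks for cycles 3-6 and then on day one of each cycle", plus end of treatment and 4-weekly post-treatment visits for patients who stopped without progressing. Once a patient has progressed, Protocol 7.2.3 provides for follow-up "after disease progression for survival and subsequent myeloma therapy until the end of study", not for further renal readings.

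Neither document sets a landmark or a time-dependent rule. The SAP names no survival test for these two comparisons; log-rank appears only under time to next therapy.

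**The concern.** A patient not on dialysis can join the recovery group only by remaining under observation until a later reading qualifies. For PFS, that waiting time is free of events by construction, yet it is credited to the recovery group. A patient who could have recovered but progresses first is counted as not recovered, with a short PFS. The comparison group therefore collects early failures whether or not recovery matters.

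OS is affected in the same direction but less, because renal readings largely stop at progression while survival time continues.

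At stake is a result that a renal-impairment trial would naturally want to report: that patients whose kidneys recovered stayed progression-free or lived longer. SAP 6.5.4 says these additional analyses are meant to give insight into a little-studied population. As planned, such a finding could appear with no association behind it. The eGFR below 15 versus 15 or more comparison in the same list uses baseline values and does not have this problem.

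**Working it through.** **Plan's own figure.** The SAP gives no figure for these comparisons. Its sample size supplies the PFS model and reproduces as follows:

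- Events = ((1.645 + 1.282)/ln(5/3))² = 32.8 (one-sided 0.05, power 90%).
- Event probability with 18 months' accrual and 30 months' follow-up is 0.994, so 32.8/0.994 = 33.0, taken up to 34.
- 34/0.90 = 37.8, so 38.

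**Inputs from the documents.** N = 38, exponential PFS with median 5 months (SAP 6.4.2), 24 months' accrual plus 13 months' follow-up (Protocol 4.1), and the Protocol Table 7.1 reading schedule.

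**Assumptions.** The share of patients able to recover, the time to recovery and post-progression survival are not in the documents and are varied.

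**Opportunity to qualify.** A patient who progresses just before Cycle 2 has had 3 scheduled post-baseline readings (Days 8, 15, 22). One who completes Cycle 6 has had 3 + 4 + 8 = 15.

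**Hand check under no association.** Take 40% able to recover, median 2 months, and read recovery continuously.

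- Hazards: progression λ = ln2/5 = 0.139; recovery ρ = ln2/2 = 0.347; sum 0.485.
- Recovery before progression: ρ/(λ+ρ) = 0.714. Seen to recover: 0.40 × 0.714 = 0.286. Able, but failed first: 0.40 − 0.286 = 0.114, all counted as not recovered.
- Recovered: S(t) = [(λ+ρ)e^(−λt) − λe^(−(λ+ρ)t)]/ρ. At t = 7.3 this is 0.497, so the median is about 7.3 months.
- Not recovered: S(t) = [0.60e^(−λt) + 0.114e^(−(λ+ρ)t)]/0.714. At t = 4.0 this is 0.505, so the median is about 4.1 months.

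Every patient has a true median of 5 months. The scheduled visits delay detection slightly, and simulation gives 7.5 and 4.0.

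**Simulation A.** Whole-period PFS comparison, no association, readings up to progression only. Cells show the hazard ratio (recovered vs not; 400,000 patients) and one-sided log-rank rejections favouring recovery (4,000 trials of 38; nominal 2.5%, the SAP's level).

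| Able to recover | Median 0.5 mo | 1 mo | 2 mo | 4 mo |
|---|---|---|---|---|
| 20% | 0.88; 3% | 0.80; 4% | 0.71; 7% | 0.62; 8% |
| 40% | 0.84; 7% | 0.76; 11% | 0.65; 18% | 0.57; 25% |
| 60% | 0.78; 12% | 0.68; 24% | 0.58; 38% | 0.50; 47% |

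For 40% able at 2 months, a median PFS of 3 months gives HR 0.60 and 24%; 5.6 months gives 0.67 and 17%. For OS (40% able, 1–4 months, median post-progression survival 5 or 10 months), HR is 0.71–0.91 and rejections are 4–10%.

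**Simulation B.** This counts one reading 28 days after progression as the end-of-treatment reading (3,000 trials per scenario; 15% of PFS events are deaths; median post-progression survival 9 months). Rejections are two-sided, nominal 5%.

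| Scenario | PFS HR; rejections | OS HR; rejections |
|---|---|---|
| 20–30% able, median 1–3 mo | 0.70–0.92; 5–11% | 0.78–0.92; 4–6% |
| 50–60% able, median 1–3 mo | 0.58–0.81; 10–34% | 0.70–0.87; 7–14% |
| 20–50% able, 30–50% chance per reading | 0.87–0.99; 5–9% | 5–6% |
| Extreme: every patient, independent 3–10% chance per reading | 0.28–0.51; 44–86% | 0.57–0.67; 15–31% |

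On the one-sided 2.5% scale, with the end-of-treatment reading, 20–30% able at 1–3 months gives PFS rejections of 4–9%. For 50% able at 2 months the figure is 15%.

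**Remedies under the same null** (rejections one-sided, nominal 2.5%):

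- Cycle 3 Day 1 landmark, patients alive and progression-free: HR 0.99–1.12 (PFS) and 0.99–1.09 (OS); rejections favouring recovery 0.6–3.3%.
- 3-month landmark: PFS HR 0.98–1.01, rejections 0.8–3.9%. For OS among all patients still in follow-up then, progressed or not, HR is 0.96–0.97.
- Time-dependent Cox: PFS HR 0.99–1.00, rejections 1.3–2.9%. OS HR is 0.85–0.94 in simulation A and 0.79–1.00 in B, with up to 10% rejections.

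**The case against.** The mechanism is hard to dispute; its size and importance are not.

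- **Low-end scenarios are plausible.** Protocol 1.3 says renal recovery is less frequent in relapsed/refractory than in newly diagnosed disease. Protocol 1.4 gives a median time to myeloma response of 0.9 months and links rapid response to renal improvement. At 20–30% able, median 0.5 months, with the end-of-treatment reading, one-sided rejections are 1.6–2.5%: no inflation. This stands. But recovery expected to follow myeloma response still comes after time zero, and with 20% able at 1–4 months simulation A gives HR 0.62–0.80.
- **The two groupings differ.** Under SAP Appendix 2, a patient with baseline eGFR 15–29 needs at least 60 to count as a renal responder, against one reading above 30 for the other grouping. The high-recovery scenarios should not be assumed for renal response.
- **Earlier analysis.** SAP 6.6 allows analysis once 20 PFS events have occurred. Cutting there lowers two-sided PFS rejection from 17.2% to 10.4% (50% able, 2 months) and from 31.7% to 17.6% (60%, 3 months). The hazard ratio stays about as biased (0.60–0.88).
- **The landmark is not free.** Its two-sided rejections run 5–9% because groups are small, and it asks about early recovery only. This supports descriptive reporting.
- **Narrow exceptions.** A dialysis patient, or one whose eGFR rose between screening and Cycle 1 Day 1, could exceed 30 at baseline. The end-of-treatment visit is timed from last dose, not progression as simulated. Neither removes the bias.
- **Exploratory status.** No survival test is named, so the rejection rates describe an assumed log-rank test. The distorted medians and hazard ratios do not depend on that test.

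**Conclusion.** The concern holds. Followed as written, both comparisons are biased towards the recovery group for PFS and, less so, for OS. The direction comes from the design.

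The size rests on assumed recovery rates and timing. With the end-of-treatment reading and 20–60% able to recover at a median of 1–3 months, PFS hazard ratios under no association run from 0.58 to 0.92 and OS from 0.70 to 0.92. The bias approaches zero when recovery is early and uncommon, or when those able to recover are very likely to show it at each reading. In the worked case the spurious gap in median PFS is 7.5 − 4.0 = 3.5 months, larger than the 5 − 3 = 2 months on which the trial is sized.

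The primary single-arm PFS analysis, the secondary endpoints and safety are unaffected. This should be corrected before the comparisons are run, but it does not threaten the trial's main conclusion.

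**What to change.** In SAP 6.5.4 and 6.6.1, for these two groupings:

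- Replace the whole-period PFS and OS comparisons with a landmark analysis at a pre-specified day, for example Cycle 3 Day 1. Include only patients alive and progression-free at that day, for OS as well as PFS, and measure time from there.
- Define renal status at the landmark: ever qualified by then, or qualifying at that visit. State how patients on dialysis (Protocol Table 7.1 schedules creatinine only for those not on dialysis) and any patient already above 30 at baseline are classified.
- Name the method (log-rank and Cox), and report the hazard ratio with its 95% CI as descriptive.
- A Cox model with recovery as a time-dependent covariate is an acceptable alternative for PFS. It should not be used for OS, because renal readings largely stop at progression and bias remains.

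The MRD-negativity subgroup in SAP 6.6.1 is also defined after baseline, and the same rule could be extended to it.

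**Cost.** SAP wording and minor programming on data already collected. Cycle 3 Day 1 is 56 days, or 1.84 months, after the start. Under a 5-month median, 38 × 0.5^(1.84/5) = 29.4 patients remain, so about 9 leave the comparison. The recovery group at that point may hold only about 2–13 patients with 20–60% able to recover at a median of 1–3 months, so precision will be low.
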